**Table 3 Clinical Laboratory Variables**

Glycaemia	Metabolism	Clinical Chemistry	Hematology	Urinalysis
Hemoglobin A 1c (HbA 1c )	Total cholesterol	Albumin	Hematocrit	Blood
Fasting plasma glucose	High density lipoprotein (HDL)-cholesterol	Alkaline phosphatase (ALP)	Hemoglobin	Glucose
Fasting serum insulin	Low density lipoprotein (LDL)-cholesterol	Alanine aminotransferase (ALT)	Mean cell hemoglobin concentration (MCHC)	Ketones
	Triglycerides	Calcium	Mean cell volume (MCV)	Leucocytes
	Uric acid	Creatinine	Platelet count	pH
		Gamma-glutamyl transferase	Reticulocytes	Protein
		Potassium	Red blood cell (RBC) count	Nitrites
		Sodium	White blood cell (WBC) count with differential count: ○ Neutrophils ○ Eosinophils ○ Basophils ○ Lymphocytes ○ Monocytes	
		Total bilirubin		
		Urea/BUN (blood/urea/nitrogen)		

The Investigator will review the laboratory results and evaluate and document whether the results are normal or abnormal and whether abnormal results are non-clinically or clinically significant. The Laboratory Report will be signed and dated by the Investigator. ‘Abnormal, clinically significant’ laboratory values will be reported as adverse events.

In case of a CV event, data on suspected CV-related abnormal laboratory findings will be delivered to the CEC Committee before the adjudication of MACE takes place (Sections 3.4.1 and 7.1.1).

Potential CV-related laboratory results will be closely followed.

[REDACTED]

[REDACTED]

[REDACTED]

[REDACTED]	[REDACTED]	[REDACTED]
[REDACTED]	[REDACTED]	[REDACTED]
[REDACTED]	[REDACTED]	[REDACTED]

[REDACTED]

#### 7.4 Handling, Storage and Destruction of Biological Samples

Blood samples will be handled in accordance with local regulations.

Central laboratories will be used for analysis of all blood samples for clinical laboratory analyses in this trial (Section 7.3.9). Sampling tubes, material for shipment of the samples, and a laboratory manual detailing all sample collection and shipment procedures will be provided and distributed to the trial sites by the central safety laboratory.

[REDACTED]

[REDACTED]

Urine samples will be analyzed at the clinic using a urine dipstick test (Section 7.3.9).

## **8 ADVERSE EVENTS**

### **8.1 Adverse Event Definition**

An adverse event is any untoward medical occurrence in a patient participating in a clinical trial. It includes:

- Any unfavorable and unintended sign, symptom or disease temporally associated with the use of the IMP, whether or not considered to be caused by the IMP.
- Adverse events commonly observed and adverse events anticipated based on the pharmacological effect of the IMP.
- Any laboratory abnormality, vital sign or finding from physical examination assessed as clinically significant by the investigator (findings from assessments and examinations done during Screening are not adverse events, but are recorded as medical history)
- Accidental injuries, reasons for any change in medication (drug and/or dose), reasons for any medical, nursing or pharmacy consultation, or reasons for admission to hospital or surgical procedures.
- Overdoses and medication errors with and without clinical consequences.

### **8.2 Collection and Recording of Adverse Events**

#### **8.2.1 Collection of Adverse Events**

The Investigator must monitor the condition of the patient throughout the trial from the time of obtaining informed consent until the last visit. Adverse events will be recorded from the time point of obtaining signed informed consent until the End-of-Trial visit. Any concomitant illnesses, other than prostate cancer, or any clinically significant signs or symptoms that are present at the Screening visit (Visit 1) will be recorded as medical history (Section 7.3.3). Adverse events that occur before administration of the first dose of IMP at Visit 2 will be regarded as pre-treatment adverse events.

The sources of adverse events cover:

- The patient's response to general questions about his health (a standard non-leading question such as "How have you been feeling since your last visit?" is asked at each visit)
- Symptoms spontaneously reported by the patient
- Investigations and examinations where the findings are assessed by the Investigator to be clinically significant changes or abnormalities
- Other information relating to the patient's health becoming known to the Investigator

#### **8.2.2 Recording of Adverse Events**

The Investigator must record all adverse events in the Adverse Event Log provided in each patient's eCRF with information about:

- Adverse event

- Date and time of onset
- Intensity
- Causal relationship to IMP
- Action taken to IMP
- Other action taken
- Date and time of outcome (time can be omitted, if applicable)
- Outcome
- Seriousness
- Relation to prostate cancer progression

Each of the items in the Adverse Event Log is described in detail in the following sections.

### **Adverse Event**

Adverse events should be recorded as diagnoses, if available. If not, separate signs and symptoms should be recorded. One diagnosis/symptom should be entered per record.

The patient may contact the trial site for an unscheduled visit due to safety reasons. The patient may also be contacted by the site for an unscheduled visit in case of an important safety signal (e.g. an abnormal laboratory value), unless he has withdrawn his consent. Any such unscheduled visits will be captured in the eCRF under unscheduled visits. Unscheduled visits are detailed in Section 6.7.

If a patient suffers from the same adverse event more than once and the patient recovers in between the events, the adverse events should be recorded separately. If an adverse event changes in intensity, a worst-case approach should be used when recording the event, i.e. the highest intensity and the longest duration of the event should be applied.b

Note the following: A procedure is not an adverse event; the reason for conducting the procedure is. Hospitalization is not an adverse event; the reason for hospitalization is. Death is not an adverse event, but the cause of death is (an exception is sudden death of unknown cause, which is an adverse event).

---

b Exception: if an adverse event with onset before the first IMP administration (i.e. a pre-treatment adverse event) changes in intensity, this must be recorded as two separate events. The initial adverse event should be recorded with outcome “not yet recovered” and the date and time of outcome is when the intensity changed. The second adverse event should be recorded with date and time of onset when the intensity changed.

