#### 9.8.2 Adverse Events

Adverse events will be tabulated by SOC and preferred term using MedDRA version 17.1 or later. The total number of patients reporting an adverse event, the percentage of patients (%) with an adverse event, and the number of events (E) reported will be presented. Adverse events will be

classified according to their intensity (using CTCAE version 4.02) and relationship to the IMP by the Investigator.

Adverse events will be regarded as 'pre-treatment' if they occur between screening and the initial injections with IMP. Adverse events which occur in the time interval from initial dosing to 3 months after (1 month=28 days) last dosing of IMP will be considered to be 'treatment-emergent'. Adverse events will be regarded as 'post-treatment' if they occur 3 months (1 month=28 days) or more after the last dosing of IMP.

Written narratives will be issued for all serious adverse events and adverse events leading to withdrawal. Missing values will be treated as missing, except for causality of adverse events to trial drug. If causality is missing, the adverse event will be regarded as being reasonably possibly related to IMP. Related adverse events (judged as being reasonably possibly related to trial drug) will be termed adverse drug reactions (ADRs).

An adverse event overview summary table will be prepared for the safety analysis set. It will display the number of patients reporting an adverse event, the percentage of patients (%) with an adverse event and the number of events reported for each treatment group. The following categories will be displayed:

- All adverse events
- Deaths
- SAEs
- Severe adverse events (CTCAE grade 3-5)
- Adverse events leading to withdrawal
- ADRs

Summary tables will be prepared for the incidence of treatment-emergent adverse events by MedDRA SOC (alphabetically) and preferred term (in decreasing frequency of occurrence). The tables will display the total number (N) of patients exposed, and the percentage of patients (%) reporting treatment-emergent adverse events. Summary tables will be prepared for:

- All adverse events
- Common adverse events (at least 5% of patients)
- Adverse events by causality (related/unrelated)
- Adverse events by intensity
- ADRs by intensity
- SAEs
- Adverse events leading to withdrawal

Supporting data listings will be provided for:

- Adverse events sorted by trial site/Investigator/patient number
- Adverse events sorted by MedDRA SOC and preferred term
- SAEs

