10.2.1 Overview of Treatment-Emergent Adverse Events

Adverse events will be regarded as 'pre-treatment' if they occur between screening and the initial injections with IMP. Adverse events which occur in the time interval from initial dosing to 3 months after (1 month=28 days) last dosing of IMP will be considered to be 'treatment-emergent'. Adverse events will be regarded as 'post-treatment' if they occur 3 months (1 month=28 days) or more after the last dosing of IMP.

An adverse event overview summary table will be prepared including the number of patients reporting an adverse event, the percentage of patients (%) with an adverse event, and the number of events (E) reported, for the following categories:

- Treatment-emergent adverse events
- Deaths
- Serious adverse events
- Adverse events leading to withdrawal
- Severe and life threatening adverse events
- Adverse drug reactions

TLF Table: Overall summary of treatment-emergent adverse events – Safety

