10.2.2 Incidence of Adverse Events

Treatment-emergent adverse events will be summarized in a table by MedDRA SOC and Preferred Term (PT). The Table will display the total number of patients reporting an adverse event, the percentage of patients (%) with an adverse event, and the number of events (E) reported. Adverse events will be presented by SOC sorted alphabetically and PT sorted in decreasing frequency of occurrence.

For each treatment the following counts are done:

- For number of patients experiencing a particular event, counting will be done by patient and not by event. This is valid for both SOC and PT, i.e., a patient will only be counted once in each SOC and once within each PT.
- For total number of events, counting will be done by event. This is valid for both SOC and PT, i.e., an event occurring more than once for the same patient will be counted for each occurrence.

Summary tables will be prepared for:

- All adverse events
- Adverse events with an incidence $[\geq 5\%]$ of patients in any treatment group
- Adverse events by causality (related/unrelated)
- Adverse events leading to death
- Adverse events by intensity
- Serious adverse events
- Adverse events leading to withdrawal

Supporting data listings will be provided for:

- All adverse events sorted by center and patient no.
- All adverse events sorted by MedDRA PT
- Serious adverse events
- Adverse events leading to death
- Adverse events leading to withdrawal.

In addition, tables summarizing all the treatment-emergent adverse events by MedDRA SOC and PT displaying the total number of patients reporting an adverse event, the percentage of patients (%) with an adverse event, and the number of events (E) reported will be provided.

TLF Table: Incidence of all adverse events by MedDRA System Organ Class and Preferred Term – Safety Analysis Set

TLF Table: Incidence of treatment-emergent non-serious adverse events (>5% cut-off) by MedDRA System Organ Class and Preferred Term – Safety Analysis Set

TLF Table: Incidence of all adverse events by causality, MedDRA System Organ Class and Preferred Term – Safety Analysis Set

TLF Table: Incidence of adverse events leading to death by MedDRA System Organ Class and Preferred Term – Safety Analysis Set

TLF Table: Incidence of all adverse events by intensity, MedDRA System Organ Class and Preferred Term – Safety Analysis Set

TLF Table: Incidence of serious adverse events by MedDRA System Organ Class and Preferred Term – Safety Analysis Set

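### A pre-treatment adverse event that partly improves after the first dose is tabulated as a new treatment-emergent event

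*Protocol*

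**What the plan says.** Protocol 8.2.2 (paragraph on recording the adverse event) has a general rule for an event whose intensity changes: "a worst-case approach should be used when recording the event, i.e. the highest intensity and the longest duration of the event should be applied". That gives one record per event.

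Footnote b makes an exception for events that began before the first IMP administration. If such an event "changes in intensity, this must be recorded as two separate events". The first record is closed with the outcome not yet recovered, and "the date and time of outcome is when the intensity changed". Then: "The second adverse event should be recorded with date and time of onset when the intensity changed".

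Classification is by timing:

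- Protocol 8.2.1: "Adverse events that occur before administration of the first dose of IMP at Visit 2 will be regarded as pre-treatment adverse events".
- Protocol 9.8.2: events "in the time interval from initial dosing to 3 months after (1 month=28 days) last dosing of IMP will be considered to be" treatment-emergent.
- SAP 10.2.1 repeats this rule: "Adverse events which occur in the time interval from initial dosing to 3 months after" the last dose, again in 28-day months.

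For the tables, SAP 10.2.2 says that "a patient will only be counted once in each SOC and once within each PT", while the event count includes every occurrence.

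**The concern.** Splitting a pre-treatment event that worsens after dosing has a clear purpose: it stops an on-treatment deterioration from being filed as pre-treatment. Splitting one that improves has no such purpose. It creates a record with a post-dose onset for an illness that began before dosing and is getting better. Neither treatment-emergent definition asks whether the patient is worse than before the first dose, and nothing else in either document removes the record.

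The incidence and intensity of adverse events is a stated safety endpoint (Protocol 2.2.2, SAP 2.2.2). What is at stake is whether the treatment-emergent tables describe what emerged on treatment, or also include partial recovery from earlier illness.

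**Working it through.** The plan gives no figure to reproduce, so the check follows the recording rule through the classification rule and the counting rule.

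**Step 1: direction of change.** The general rule and footnote b use the same verb for a change in intensity. The general rule settles the change by keeping the highest grade, so it covers falls as well as rises. Nothing narrows the exception to rises.

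**Step 2: onset.** The Protocol 8.2.2 paragraph on onset dates an event from when its first signs or symptoms were noticed. For an improving pre-treatment event that is before dosing. Footnote b replaces this with the date of change. The outcome list in 8.2.2 already has a category for a patient who is recovering, so improvement can be recorded without a second record.

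**Step 3: classification and count.** Each case below is an event that starts after consent and before the first dose. The last two columns give the number of treatment-emergent records under the current text and under a rule that requires a higher grade than the pre-treatment record.

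| Case | Records under footnote b | Current | With rule |
|---|---|---|---|
| Grade 3, falls to 1 after first dose | Grade 3 before dosing; grade 1 with onset after dosing | 1 | 0 |
| Grade 1, rises to 3 after first dose | Grade 1 before dosing; grade 3 with onset after dosing | 1 | 1 |
| Intensity changes before first dose only | Both have onset before dosing | 0 | 0 |
| Resolves with no intermediate grade | One record, closed as recovered | 0 | 0 |
| Grade 2, falls to 1, then rises to 3, all after first dose | Grade 2 before dosing; second record, kept at its highest grade, 3 | 1 | 1 |

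The last row rests on a reading of 8.2.2. The second record begins after dosing, so the footnote no longer applies to it and the general worst-case rule does. A later rise above the pre-dose grade is therefore not lost.

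Only the first row is misclassified. It always adds one event. Under SAP 10.2.2 it adds a patient to a preferred term or system organ class only if he has no other treatment-emergent event there.

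**Step 4: effect on a comparison.** Take equal arms of n patients, with a and b patients counted correctly, and k false additions in each arm.

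- Difference: (a + k)/n − (b + k)/n = (a − b)/n, which is unchanged.
- Ratio: (a + k)/(b + k), which lies closer to 1 than a/b when k > 0 and a ≠ b.

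**The case against.** The strongest reply is that the affected group is very narrow. Conditions present at screening, and findings from screening assessments, are medical history (Protocol 7.3.3, 8.1, 8.2.1). The footnote reaches only events that start after consent, in a window of at most 21 days (Protocol 6.2), and are still present at the first dose. Such an event must then improve in part: full resolution is an outcome, and a grade 1 event cannot step down. This limit stands, and it sets the size of the point.

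A second reply is that the plan over-includes safety data on purpose. SAP 10.2 treats missing causality as related, missing intensity as severe and missing seriousness as serious. But those rules fill gaps in the data. Here the dates and grades are known, and the record is classified against what they show. It is also fair that splitting preserves the pre-dose grade, which a single worst-case record would lose. The fix leaves the split in place and changes only the classification.

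Three stronger readings are tempting, and the documents do not support them.

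- A reader might want a number of affected patients. Neither document gives the rate of events ongoing at first dose or the share that improve stepwise. The 545 in SAP section 3 are randomized patients, whereas the safety set is treated patients.
- A reader might infer that a serious pre-treatment event becomes a treatment-emergent serious event when it improves. Seriousness is an item of each record (Protocol 8.2.2), and nothing says it is copied to the second one.
- A reader might infer that the comparison between arms is pulled towards no difference in general. With equal additions and equal arms, Step 4 shows that only ratios move. SAP 10.2 plans counts and percentages with no test between arms.

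**Conclusion.** The point holds as a classification error. The recording rule and the timing-only definition together count a partly improving pre-treatment event as treatment-emergent, and neither document corrects this. It rests on reading the footnote as written, with no direction of change.

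The effect is limited to descriptive adverse-event tables. In the intensity table the false record enters at the lower grade. The effect is probably small and cannot be quantified from the documents. Adjudicated MACE, and so the primary analysis, is untouched. The rule is worth correcting because it gives a wrong count for a stated endpoint and the correction is cheap, not because it threatens the trial's conclusions.

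**What to change.** Add to SAP 10.2.1, and list in SAP section 12 as a change from Protocol 9.8.2, that a record which continues a pre-treatment event is treatment-emergent only if its CTCAE grade is higher than that of the pre-treatment record. Otherwise, leave it out of the treatment-emergent tables and keep it in the listings.

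The log items in Protocol 8.2.2 include no link between the two records, so the SAP should define the pair as:

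- the same patient and the same preferred term;
- the first record's outcome is not yet recovered;
- the first record's outcome date equals the second record's onset date. Match on date only, because the outcome time may be omitted.

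A record that cannot be paired stays treatment-emergent by default.

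SAP section 3 says that the trial was terminated early, and editing the footnote would not change records already made under it. The SAP rule is therefore the working remedy. If the footnote is reused, its trigger should read *increases in intensity after the first IMP administration*.

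The cost is a small matching step in programming and slightly lower event counts. No new data are needed, and a worsening above the pre-dose grade is still counted.

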## **Date and Time of Onset**

The date and time of onset is the date and time when the first sign(s) or symptom(s) were first noted. If the adverse event is an abnormal clinically significant laboratory test or outcome of an examination, the onset date is the date the sample was taken or the examination was performed.

## **Intensity / Common Terminology Criteria for Adverse Events Grading Scale**

The Investigator must grade each adverse event according to the National Cancer Institute (NCI) Common Terminology Criteria for Adverse Events (CTCAE) (version 4.02). According to this guidance document all adverse events are rated on a 5-point scale corresponding to mild, moderate, severe, life-threatening or disabling and death. The guidance document will be provided to each trial site.

Each adverse event must be graded according to the specific criteria for grading as described in the CTCAE. For events not described in the CTCAE the following criteria will be used:

- Grade 1: Mild (minor; no specific medical intervention; asymptomatic laboratory findings only; marginal clinical relevance)
- Grade 2: Moderate (minimal intervention: local intervention; non-invasive intervention)
- Grade 3: Severe (significant symptoms, requiring hospitalization or invasive intervention; transfusion; elective interventional radiological procedure; therapeutic endoscopy or operation)
- Grade 4: Life-threatening or disabling (complicated by acute, life-threatening metabolic or CV complications such as circulatory failure, hemorrhage, sepsis. Life-threatening physiologic consequences; need for intensive care or emergent invasive procedure; emergent interventional radiological procedure, therapeutic endoscopy or operation)
- Grade 5: Death

## **Causal Relationship to IMP**

The possibility of whether the IMP caused the adverse event must be classified as one of the following:

- Reasonable possibility:  
There is evidence or argument to suggest a causal relationship between the IMP and the adverse event. The adverse event may occur as part of the pharmacological action of the IMP or may be unpredictable in its occurrence.

Examples:

- Adverse events that are uncommon but are known to be strongly associated with IMP exposure.
- Adverse events that are not commonly associated with IMP exposure, but the event occurs in association with other factors strongly suggesting causation, such as a strong temporal association or the event recurs on rechallenge.

- No reasonable possibility:  
There is no reasonable evidence or argument to suggest a causal relationship between the IMP and the adverse event.  
Examples:
  - Known consequences of the underlying disease or condition under investigation.
  - Adverse events common in the trial population, which are also anticipated to occur with some frequency during the course of the trial, regardless of IMP exposure.

### **Action Taken to IMP**

The action taken to the IMP in response to an adverse event must be classified as one of the following:

- No change (medication schedule maintained or no action taken)
- Withdrawn
- Interrupted, e.g. in case of hospitalization

